 Performance status: 0 - Subject is fully active and able to continue with predisease activities without restrictions. 1 - Subject is restricted from physically strenuous activity but is ambulatory and can perform light or sedentary work. 2 - Subject is ambulatory and performs self-care but is unable to work; subject is up and about for more than 50% of waking hours. 3 - Subject can perform only limited self-care; subject is confined to bed or chair for 50% or more of waking hours. 4 - Subject is completely disabled and unable to carry out any self-care; subject is totally confined to bed or chair. 5 - Dead.

Listing 16.2.13.1
 PK concentrations of Mogamulizumab

Treatment = Phase 1: Dose finding phase (Mogamulizumab 1 mg/kg + Nivolumab 240 mg)

Subject	Cancer Type	Cycle Timepoint	Last Prior		Time from Last Dose (Days)	PK Collection Date/Time (Days [1])	PK Concentration (ng/mL)
			Mogamulizumab Dose Date and Time (Days [1])	Mogamulizumab Dose Date (Days [1])			
xxx-xxx	Liver	Cycle 1 Day 1 (Pre)	YYYY-MM-DD HH:MM - HH:MM	YYYY-MM-DD (xx)	xx	YYYY-MM-DD HH:MM (xx)	BLQ
		Cycle 1 Day 1 (Post)				YYYY-MM-DD HH:MM (xx)	xx
		Cycle 2 Day 1 (Pre)	YYYY-MM-DD HH:MM - HH:MM	YYYY-MM-DD (xx)	xx	YYYY-MM-DD HH:MM (xx)	NA
		Cycle 2 Day 1 (Post)				YYYY-MM-DD HH:MM (xx)	xx

Continue with Expansion phase (Mogamulizumab x mg/kg + Nivolumab 240 mg).

BLQ (Below Limit of Quantification): Concentration <12.5 ng/mL

NA: Not applicable because of lack of the sample

[1] Days = Date of Evaluation - Date of First Dose of the Study Drug (+1 if Date of Evaluation ≥ First Dose Date of the Study Drug).
 Time from last dose of study drug is calculated relative to the PK collection date.

Listing 16.2.14.1.1
 Anti-Drug Antibody Response to Mogamulizumab by Collection Time

Treatment = Phase 1: Dose finding phase (Mogamulizumab 1 mg/kg + Nivolumab 240 mg)

Subject	Cancer Type	Cycle	ADA Sample Collected?	Sample Date/Time (Days [1])	Assay				PK Concentration (ng/mL)
					Screening	Confirmatory	ADA Status [2] (Titer)	Neutralizing	
xxx-xxx	Liver	Cycle 1 Day 1	Yes	YYYY-MM-DD HH:MM (xx)	Negative	---	Inconclusive	---	17000
		Cycle 2 Day 1	No						
		Cycle x Day 1	Yes	YYYY-MM-DD HH:MM (xx)	Positive	Positive	Positive (16)	Negative	xxx
		100-110 Days Post Last Dose Follow-up	Yes	YYYY-MM-DD HH:MM (xx)	Negative	---	Unknown	---	xxx

Continue with Expansion phase (Mogamulizumab x mg/kg + Nivolumab 240 mg).

BLQ = Below lower limit of quantification.

[1] Days = Sample Date - Date of First Dose of the Study Drug (+1 if Sample Date ≥ First Dose Date of the Study Drug).

[2] ADA status is positive when the sample is positive in the confirmatory assay. ADA status is negative when the sample is negative in the screening assay and the serum mogamulizumab concentration at the same time point is equal to or less than the drug tolerance limit (16000 ng/mL), or the sample is positive in the screening assay and negative in the confirmatory assay. ADA status is "Inconclusive" when screening result is "Negative" and the PK concentration of mogamulizumab at the corresponding timepoint is above the drug tolerance level of the assay (>16000 ng/mL); if screening result is "Positive", the ADA status is the same as confirmatory result regardless of the PK concentration of mogamulizumab at the corresponding timepoint. ADA status is "Unknown" when screening result is "Negative" and the PK concentration of mogamulizumab at the corresponding timepoint is unknown.

Listing 16.2.14.1.2
Subject Status of Anti-Drug Antibody Response to Mogamulizumab

Treatment = Phase 1: Dose finding phase (Mogamulizumab 1 mg/kg + Nivolumab 240 mg)

Subject	Cancer Type	Time Point	ADA/NAb Status
xxx-xxx	Liver	Baseline	Negative
		Overall Post Baseline	Positive
		Neutralizing	Negative

Continue with Expansion phase (Mogamulizumab x mg/kg + Nivolumab 240 mg).

Listing 16.2.14.2.1
 Anti-Drug Antibody Response for Subjects with Infusion Reactions to Mogamulizumab

Treatment = Phase 1: Dose finding phase (Mogamulizumab 1 mg/kg + Nivolumab 240 mg)

Subject	Cancer Type	Assay Positive at Any Time			Adverse Event Reported	Grade	Onset Date and Time/ Day [1]	Duration (Days [2])	Discontinued or Dose Interrupted?
		Screening	Confirmatory	Neutralizing					
xxx-xxx	Liver	Yes	No	No	Infusion Reaction	1	YYYY-MM-DD HH:MM/xx	4	No
					xxxxxxxxxx	2	YYYY-MM-DD/xx	2	Yes
xxx-xxx					Infusion Reaction	1	YYYY-MM-DD/xx	1	No

Continue with Expansion phase (Mogamulizumab x mg/kg + Nivolumab 240 mg).

[1] Day = Start date of adverse event - First dose date of the study drug (+1 if Start ≥ First dose date of the study drug)

[2] Duration = Stop date of adverse event - Start date of adverse event + 1.

Note: Infusion reactions are identified by the preferred term infusion related reaction, regardless of the investigator assessment of relationship to study drug.

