- 12) Subject has any unresolved toxicity Grade > 1 (defined by Common Terminology Criteria for Adverse Events version 4.03 [CTCAE v. 4.03]) from previous anti-cancer therapy, excluding alopecia, fatigue, and laboratory values listed in the inclusion criteria. Subjects with irreversible toxicity that is not reasonably expected to be exacerbated by the investigational product may be included (e.g., hearing loss) at the discretion of the Investigator;
- 13) Subject use of immunosuppressive medication within 14 days before Cycle 1 Day 1. Note: Inhaled, ocular, intranasal, intra-articular, or topical corticosteroids are allowed. Non immunosuppressive doses of systemic steroids for adrenal replacement or for contrast allergy are allowed;
- 14) Subject has an active autoimmune disease or a history of autoimmune disease which may affect vital organ function or require immune suppressive treatment including systemic corticosteroids; these include but are not limited to subjects with a history of immune-related neurologic disease, multiple sclerosis, uveitis, autoimmune (demyelinating) neuropathy, Guillain-Barré syndrome, myasthenia gravis; transverse

myelitis; systemic autoimmune disease such as systemic lupus erythematosus, connective tissue diseases, scleroderma, autoimmune hepatitis;

- a) Exceptions: Subject with vitiligo, alopecia, type I diabetes mellitus, and endocrine deficiencies including hypothyroidism managed with replacement hormones including physiologic corticosteroids are eligible. Subject with psoriasis controlled with topical medication, or conditions not expected to recur in the absence of an external trigger (precipitating event) are eligible;
- 15) Subject has a history of toxic epidermal necrolysis or Stevens-Johnson syndrome;
- 16) Subject has a history of inflammatory bowel disease, Crohn's disease, ulcerative colitis, or Wegener's granulomatosis;
- 17) Subject has primary or acquired immunodeficiency or known history of testing positive for human immunodeficiency virus (HIV) or known acquired immunodeficiency syndrome;
- 18) Subject who tests positive for hepatitis B surface antigen (HBVsAg) or hepatitis C RNA indicating acute or chronic infection except for subjects with hepatocellular carcinoma;
- 19) Subject has another active malignancy requiring concurrent intervention;
- 20) Subject who is receiving any other investigational agents;

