### **8.5 Concomitant Treatments**

Any medication(s), including those taken within 30 days prior to the first dose of IMPs, throughout treatment with IMP, until the 30-day follow-up visit after the last dose of IMP or

until start of new anticancer therapy (whichever occurs first), and anytime thereafter if used to treat IMP-related SAEs will be recorded.

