4.7.4 Other Prior/Concomitant Medications

Prior and concomitant medications will be coded using the World Health Organization (WHO) Drug Dictionary (version September 2015). Prior medications include medications that were taken within 30 days prior to the first dose of IMP. Concomitant medications during the treatment period include medications that started at any time and were taken at any time after the start of IMP until 30 days after the last dose of IMP.

The number and percentage of subjects taking prior medications or concomitant medications during the treatment period will be summarized by anatomical therapeutic chemical (ATC) and preferred term (PT) for the Safety Analysis Set. If a subject takes more than one medication in the same ATC class, the subject will be counted only once within that classification. The same subject may contribute to two or more preferred terms within the same ATC classification.

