6.2.4 Prior and Concomitant Medications

- 1) Prior and concomitant medications will be coded and classified using the World Health Organization (WHO) Drug Dictionary (version September 2015). The specific dictionary version will appear in the actual tables/listings.
- 2) Counting rules for prior/concomitant medications: Prior medications include medications that were taken within 30 days prior to study entry. Concomitant medications during the treatment period include medications that started at any time and were taken at any time after the start of IMP until 30 days after the last dose of the IMP.
- 3) Medications missing both start and stop dates, or having a start date prior to 30 days post the last dose of IMP and missing the stop date, or having a stop date after the start of IMP and missing the start date, will be counted as concomitant. When partial dates are present in the data, both a partial start date and/or a partial stop date will be

evaluated to determine whether it can be conclusively established that the medication either ended prior to the start of IMP or started after 30 days post the last dose of IMP. If the above cannot be conclusively established based on the partial and/or present dates, then the medication will be counted as concomitant.

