Note: Percentage is calculated using the number of subjects in the column heading as the denominator. WHO Drug Dictionary (September, 2015) was used for coding Medications that started at any time until 30 days after the last dose date, and were taken at any time after the first dose date are presented.

Programming note: First page of the table is for "All Cancer Types". Subsequent pages are for NSCLC SQ, NSCLC NSQ PD-L1 non-expressing, Ovarian, CRC, SCCHN, HCC, Pancreatic cancer types separately.

Repeat for the following:

Table 14.1.2.5.1
 Summary of Prior Cancer Therapy
 Safety Analysis Set

Table 14.1.2.5.2
 Summary of Post Treatment Cancer Therapy
 Safety Analysis Set

Table 14.1.2.6.1
 Summary of Prior Steroids and Immune Modulating Medications by Reason for Administration
 Safety Analysis Set

[Note: Use Reasons: Medical History Condition, Prophylaxis, Adverse Event]

All Cancer Types: Reason for administration = Medical History Condition

ATC Classification	Mogamulizumab x mg/kg + Nivolumab 240 mg N=xxx
Preferred Term	n (%)
Any Subjects with Prior Steroid and Immune Modulating Medication, Total	xx (xx.x)
ATC Classification 1	xx (xx.x)
Preferred Term 1	xx (xx.x)
Preferred Term 2	xx (xx.x)
Preferred Term 3	xx (xx.x)

Followed by

[All Cancer Types: Reason for administration = Prophylaxis]

[All Cancer Types: Reason for administration = Adverse Event]

Programming note: Add footnote "Medications with start dates within 30 days of the first dose date of the study treatment, and ended prior to the first dose date of the study treatment are presented."

Table 14.1.2.6.2
 Summary of Concomitant Steroids and Immune Modulating Medications by Reason for Administration
 Safety Analysis Set

[Note: Use Reasons: Medical History Condition, Prophylaxis, Adverse Event. Add footnote: Medications that started at any time until 30 days after the last dose date, and were taken at any time after the first dose date are presented.]

Table 14.1.2.6.3
 Summary of Prior Steroids and Immune Modulating Medications by Route of Administration
 Safety Analysis Set

[Note: Use Systemic Use, Topical. Defined as

Systemic = (Oral, Intravenous, Injection, Intrahepatic, Nasogastric, Intramuscular, Intrapleural, INTRAMUSCULAR, Subcutaneous, Epidural)

Topical = (Topical, Intraocular, Nasal, Respiratory, Rectal, Vaginal, Transdermal, Sublingual)

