[1] Days = Post treatment discontinuation cancer therapy start date - date of the first dose + 1. If the month and year of the treatment start are provided but the day is missing, the missing day is imputed as 15. If only the year is provided, no imputation shall be performed.

* Days calculation is based on imputed start date.

Note: WHO Drug Dictionary (September, 2015) was used for coding.

Listing 16.2.4.10
 Prior Medication (Excluding Cancer Therapy)

Treatment = Phase 1: Dose finding phase (Mogamulizumab 1 mg/kg + Nivolumab 240 mg)

Subject	Cancer Type	VT: Verbatim Term PT: Preferred Term ATC: ATC Class	Indication	Start Date (Days [1])/ Stop Date (Days [1])	Total Daily Dose (Unit)	Frequency/Route
xxx-xxx	Liver	VT: xxxxxxxxxxxxxxxx PT: xxxxxxxxxxxxxxxx [Original: xxxx] ATC: xxxxxxxxxxxxxxxx	xxxx	YYYY-MM-DD (xx)/ YYYY-MM-DD (xx)	xxxx (xx)	xxxx
xxx-xxx	Renal Cell	VT: xxxxxxxxxxxxxxxx PT: xxxxxxxxxxxxxxxx ATC: xxxxxxxxxxxxxxxx	xxxx	YYYY-MM (-)/ YYYY (-)	xxxx (xx)	xxxx
xxx-xxx	Sarcoma	VT: xxxxxxxxxxxxxxxx PT: xxxxxxxxxxxxxxxx ATC: xxxxxxxxxxxxxxxx	xxx	YYYY-MM-DD (xx)/ YYYY-MM (-)	xxxx (xx)	xxxx

Continue with Expansion phase (Mogamulizumab x mg/kg + Nivolumab 240 mg).

[1] Days = Date of Start/Stop of Medication - Date of First Dose of the Study Drug (+1 if Start/Stop Date of medication ≥ First Dose Date of the Study Drug).

- = Not available. [Original] is in reference to the coded medication preferred terms according to WHO Drug Dictionary without collapsing of terms. [PT] is presenting the collapsed terms, used for summaries.

* Medication ended prior to 30 days before the first dose date of the study drug.

Note: WHO Drug Dictionary (September, 2015) was used for coding. All medications started prior to the first dose date of the study drug are listed. Medications taken within 30 days of the first dose date of the study drug, and ended prior to the first dose date of the study drug are summarized in the table.

Listing 16.2.4.11
 Concomitant Medication (Excluding Cancer Therapy)

Treatment = Phase 1: Dose finding phase (Mogamulizumab 1 mg/kg + Nivolumab 240 mg)

Subject	Cancer Type	VT: Verbatim Term PT: Preferred Term ATC: ATC Class	Start Date (Days [1])/ Stop Date (Days [1])	Total Daily Dose (Unit)	Frequency/Route
xxx-xxx	Liver	VT: xxxxxxxxxxxxxxxx PT: xxxxxxxxxxxxxxxx ATC: xxxxxxxxxxxxxxxx	YYYY-MM-DD (xx)/ YYYY-MM-DD (xx)	xxxx (xx)	xxxx

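### Three prior-medication table footnotes select drugs by start date rather than by use in the 30-day window, so some recently stopped drugs appear in no summary table

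*SAP*

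**What the plan says.** Four places describe the window by use of the drug:

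- Protocol 8.5 has sites record medications, "including those taken within 30 days prior to the first dose of IMPs".
- SAP 4.7.4: "Prior medications include medications that were taken within 30 days prior to the first dose of IMP".
- SAP 6.2.4 also goes by use, but from a different date: "Prior medications include medications that were taken within 30 days prior to study entry".
- The note to Listing 16.2.4.10 says which of the listed drugs the table summarizes: "Medications taken within 30 days of the first dose date of the study drug, and ended prior to the first dose date".

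The footnotes to Tables 14.1.2.4.1, 14.1.2.6.1 and 14.1.2.6.3 describe it by start date: "Medications with start dates within 30 days of the first dose date of the study treatment, and ended prior to the first dose date".

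The matching concomitant tables (14.1.2.4.2, 14.1.2.6.2 and 14.1.2.6.4) show drugs begun at any time up to 30 days after last dose that "were taken at any time after the first dose date are presented".

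Protocol 7.3, exclusion criterion 13, bars "Subject use of immunosuppressive medication within 14 days before Cycle 1 Day 1". It allows inhaled, ocular, intranasal, intra-articular and topical corticosteroids, and non-immunosuppressive systemic doses for adrenal replacement or contrast allergy.

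**The concern.** A programmer working from the shells will apply the footnote, not SAP 4.7.4. The tables will then not contain what the SAP text says they contain, and the note to Listing 16.2.4.10 will misdescribe its own table. The prior and concomitant rules also stop meeting: a drug can be used inside the 30-day window and be counted by neither.

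The sponsor planned separate prior-steroid tables by reason and by route, so it evidently wants recent steroid and immune-modulating use described for two agents that Protocol 8.2.3 treats as immuno-oncology drugs. Those tables would read low.

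**Working it through.** No figure in the plan needs reproducing; this is a comparison of selection rules. Let s be the start day and e the stop day of a course, with negative days before first dose, as in SAP 6.2.2. Only courses begun before first dose matter here.

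| Source | Condition |
|---|---|
| SAP 4.7.4 | e ≥ -30 (no condition on s, and none that the course has ended) |
| Listing 16.2.4.10 note | -30 ≤ e ≤ -1 |
| Footnotes to the three prior tables | s ≥ -30 and e ≤ -1 |
| Concomitant tables | use after first dose, so e not before first dose |

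**What is lost.** Courses that meet 4.7.4 but neither the footnotes nor the concomitant rule have e ≥ -30, e ≤ -1 and s < -30. That is every course begun on Day -31 or earlier and stopped on Days -30 to -1. With start days taken back to Day -365, this is 335 start days × 30 stop days = 10,050 start/stop combinations, all lost.

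**Direction.** A course with s ≥ -30 and e ≤ -1 has e ≥ s ≥ -30, so it also meets 4.7.4 and the listing note. The footnotes never admit a drug that the text would exclude. The error is an undercount only.

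**Examples.**

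| Course | 4.7.4 | Listing note | Footnotes | Concomitant |
|---|---|---|---|---|
| Day -180 to -15 | yes | yes | no | no |
| Day -60 to -20 | yes | yes | no | no |
| Day -31 to -16 | yes | yes | no | no |
| Topical, Day -365 to -1 | yes | yes | no | no |
| Day -25 to -16 | yes | yes | yes | no |
| Day -90 to +10 | yes | no | no | yes |
| Day -90 to -40 | no | no | no | no |

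The first four rows are the gap. The sixth shows a second mismatch: 4.7.4 does not require the drug to have ended, while the listing note and the footnotes do. That course is still reported, as concomitant.

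**Eligibility.** Criterion 13 excludes immunosuppressive use in the 14 days before Cycle 1 Day 1. For compliant subjects, lost courses at immunosuppressive doses are therefore those stopped on about Days -30 to -15. Permitted local-route or replacement steroids need no washout and can be lost up to Day -1. The Topical group in Table 14.1.2.6.3 includes nasal and respiratory routes, so it is directly exposed.

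**Scale.** The documents do not say how many subjects have such a course. Each subject wholly missed in a row lowers its percentage by 1/N. At the planned maximum of 188 that is 1/188 = 0.5 points. On the tumor-type pages of Table 14.1.2.4.1, with planned cohorts of 17 to 36, it is between 1/36 = 2.8 and 1/17 = 5.9 points. A subject with another qualifying course in the same row is not missed.

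**Anchor date.** SAP 6.2.4 counts back from study entry, which the SAP does not define. If it meant consent, the window could sit up to 28 days earlier than in 4.7.4, since Protocol 6.3 allows a 28-day screening period. If it meant first dose, nothing changes.

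**The case against.** The best reply is that this is a wording slip with little consequence, and much of that reply stands.

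- The listing note suggests that the sponsor meant use in the window. The drugs also stay visible by subject. Listing 16.2.4.10 states: "All medications started prior to the first dose date of the study drug are listed". Listing 16.2.4.12 flags only drugs that ended more than 30 days before first dose, so it appears to keep the affected steroids too.
- Other criteria in Protocol 7.3 shrink the pool. Subjects with treated CNS metastases must be off corticosteroids for 4 weeks before enrollment (criterion 4). Most cancer therapy must have stopped 28 days earlier (criterion 5). Autoimmune disease that may need systemic corticosteroids is largely excluded (criterion 14).
- No planned efficacy or safety analysis uses these tables as a covariate, subgroup or exclusion.

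What does not stand is that the listing note settles the matter. The start-date condition is written into three footnotes and would be programmed three times.

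A reader might also infer that the tables drop the subjects with the longest steroid exposure and keep only short new courses. The documents do not support that: a long course still running at first dose is counted in the concomitant tables, and only courses that ended before dosing are lost. Nor do they support any estimate of how many subjects are affected.

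**Conclusion.** The inconsistency is real and minor. As written, the three footnotes contradict SAP 4.7.4, SAP 6.2.4 and the Listing 16.2.4.10 note, and drugs begun before Day -30 and stopped on Days -30 to -1 drop out of every prior and concomitant summary table. Counts can only be too low, by an amount that the documents do not allow anyone to compute. The effect is confined to descriptive tables on the Safety Analysis Set; no response rate, survival estimate or error rate changes. This rests on the shells being programmed as footnoted, and the Day -15 limit rests on subjects complying with criterion 13.

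**What to change.** Use one rule throughout: *taken at any time in the 30 days before the first dose of IMP, whatever the start date, and stopped before the first dose*.

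- **SAP 4.7.4:** add the condition that the drug stopped before first dose. Without it, the text and the corrected tables would still differ for drugs continuing past first dose.
- **SAP 6.2.4:** make the same change, and replace study entry with first dose of IMP.
- **Footnotes to Tables 14.1.2.4.1, 14.1.2.6.1 and 14.1.2.6.3:** replace the start-date condition with this rule.
- **Notes to Listings 16.2.4.10 and 16.2.4.12:** use the same words.

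Every drug used in the window is then counted as prior if it stopped before first dose and as concomitant if it continued. The cost is a few lines of text and one selection condition in the program. Protocol 8.5 already has the data collected.
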